**Methods of assessment:**

- 1- Pre-operative T1 and postoperative T2 lateral cephalometric radiographs measures are compared and assessed.
- 2- Pre-operative and postoperative casts are compared and assessed.
- 3- Pre-operative and postoperative smile photographs are compared and assessed.
- 4- Calculation of The total period of elastics wear till the class I canine relationship achieved for both groups is compared and assessed.

	Outcome	Measuring tool	Measuring unit
Primary outcome	
 
• Upper incisor inclination (UI/PP) and (U1/SN).
 
• Upper incisors inclination and position (U1/NA)
 
	
 
• Lateral cephalometry.
 
• Lateral cephalometry.
 
	
 
• Degree
 
• Degree/mm
 

Secondary outcomes	
 
• Lower incisor inclination (LI/MP).
 
• Lower incisors inclination and position (L1/NB)
 
• Occlusal plane inclination (anatomical occlusal plane).
 
	
 
• Lateral Cephalometry
 
• Lateral cephalometry.
 
• Lateral cephalometry
 
	
 
• Degree
 
• Degree/mm
 
• Degree
 

--------------------	--	---	---

	
Op/(Me-Go) Op/FH Op/AB
 
 
• Mandible to cranial base (SNB)
 
• Mandible to cranial base (Pg to N perpendicular to FH).
 
• Maxilla to cranial base (SNA).
 
• Maxilla to cranial base (point A to N perpendicular to FH).
 
• ANB angle.
 
• FH, palatal and SN planes to mandibular plane angles.
 
• Ar Go Me
 
• ANS Me
 
• S Go
 
	
 
• Lateral cephalometry.
 
• Lateral cephalometry.
 
• Lateral cephalometry
 
• Lateral cephalometry.
 
• Lateral cephalometry.
 
• Lateral cephalometry.
 
• Lateral cephalometry.
 
• Lateral cephalometry
 
• Lateral cephalometry
 
	
 
• Degree
 
• mm
 
• Degree
 
• Mm
 
• Degree
 
• Degree
 
• Degree
 
• Mm
 
• mm
 

--	---	--	--

	

• Time of elastic wear

	Standardized extraoral photos	

• Months /days

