### **Objective**

The aim is to compare the effect of immediate light short elastics versus conventional elastics on the Inclination of upper incisors in patients with canine class II malocclusion.

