### **Methodology**

#### **Study population:**

This prospective clinical trial will be conducted on 30 patients both gender , divided into 2 groups:

Group 1: fifteen patients will wear immediate light short Class II elastics.

Group 2: fifteen patients will wear conventional elastics.

Selected from the outpatient clinic of the Orthodontic Department, Faculty of Dentistry, Ain Shams University.

The subjects will be selected to fulfill the following inclusion criteria:

- 1- Canine class II malocclusion.
- 2- Patients with permanent dentition.
- 3- Increased overjet.
- 4- Non extraction.

Exclusion criteria:

- 1- Gummy smile.
- 2- Gingival recession.
- 3- Vulnerable patients.

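### The primary incisor comparison is worded as T1 versus T2 rather than between arms, and the T1–T2 interval covers different treatment phases in the two groups

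*Protocol*

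**What the plan says.** The Protocol's Objective is to "compare the effect of immediate light short elastics versus conventional elastics on the Inclination of upper incisors". The closing paragraph of the Introduction states the same contrast between regimens, and item 2 under Procedure allocates patients at random. Study population puts fifteen patients in each group.

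Methods of assessment has four items. Item 1 covers the radiographs, which supply the primary outcome ("Upper incisor inclination (UI/PP) and (U1/SN" together with U1/NA): "Pre-operative T1 and postoperative T2 lateral cephalometric radiographs measures are compared and assessed". Items 2 and 3 say the same of casts and smile photographs. Only item 4, the duration of elastic wear, mentions the groups: it runs "till the class I canine relationship achieved for both groups is compared and assessed". The outcome table gives tools and units. It does not say whether the endpoint is the T2 value or the change, and it names no contrast between arms.

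On timing, item 10 under Procedure takes the paired records before elastic wear and again when canine class I is reached. Under items 5 and 6, group 1 starts elastics straight after bonding and the initial wire. Group 2 starts only on reaching the passive 0.016x0.022 inch stainless steel wire. Separately, Study procedure and item 1 under Procedure provide a full set of initial records, including a lateral cephalogram, for every patient.

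**The concern.** There are two linked problems.

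First, the comparison stated for the primary outcome is a before/after contrast that names no arm, whereas the question is which regimen does what to the incisors. An analyst working from these lines could run a paired test in each arm and read a result that is significant in one arm but not the other as a treatment difference. That inference is unsound and, with 15 per arm, often wrong.

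Second, even an analyst who compares T1–T2 change between arms inherits an unequal interval. If T1 is the item 10 record, the group 2 starting point lies after randomisation and has already been moved by alignment. The two changes then measure different things, and randomisation no longer protects the contrast.

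**Working it through.** **Inputs.** From the Protocol: 15 patients per group. The Protocol gives no alpha, SD, effect size or correlation, so there is no planned figure to reproduce. Assumed: two-sided alpha 0.05; the same true mean change d in both arms, in units of the SD of change; baseline–T2 correlation r of 0.5 or 0.8.

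**Step 1: separate tests in each arm.** Let p be the power of a paired t test with n = 15 (noncentral t, 14 df, noncentrality d√15). With independent arms and equal true change, the chance that exactly one arm is significant is 2p(1−p).

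| d (SD of change) | p | 2p(1−p) |
|---|---|---|
| 0 | 0.050 | 0.095 |
| 0.3 | 0.192 | 0.310 |
| 0.5 | 0.438 | 0.492 |
| 0.545 | 0.502 | 0.500 |
| 0.8 | 0.821 | 0.294 |
| 1.0 | 0.949 | 0.097 |
| 1.2 | 0.991 | 0.019 |

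Simulation with 200,000 trials per setting gave 9.4% at d = 0, 49.8% at d = 0.53 and 31.5% at d = 0.78. A direct between-arm t test on change (28 df) gave 5.0%, 5.1% and 5.0% in the same settings.

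**Step 2: what T1–T2 change contains.** As a simple additive sketch, let A be the incisor change from alignment and E the change from elastics.

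- Group 1, from bonding to canine class I: A₁ + E₁, with A₁ being whatever alignment occurs by T2.
- Group 2, from the working wire to canine class I: E₂ only.
- Difference in change: (A₁ + E₁) − E₂. If the elastics act identically (E₁ = E₂), this equals A₁, not zero.
- Measured from the pre-bonding film in both arms: (A₁ + E₁) − (A₂ + E₂), which is the contrast between the two randomised regimens.

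The Protocol has no data on the size of A₁, so this distortion cannot be quantified.

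**Step 3: precision of the between-arm options.** Half-widths of the 95% CI are in units of the SD of a single measurement, taken as equal at baseline and T2, with the same baseline film in each method.

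- T2 alone: t(0.975, 28) × √(2/15) = 2.048 × 0.365 = 0.748.
- Change score: 0.748 × √(2(1−r)) = 0.748 at r = 0.5; 0.473 at r = 0.8.
- ANCOVA: 0.748 × √(1−r²) = 0.648 at r = 0.5; 0.449 at r = 0.8.

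The gain over a change score is 1 − 0.648/0.748 = 13% at r = 0.5 and 1 − 0.449/0.473 = 5% at r = 0.8. The degree of freedom spent on the covariate alters these half-widths by less than 0.002 SD.

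**The case against.** The strongest reply is that no analysis has been fixed at all. The items sit under Methods of assessment, directly above a table of tools and units, and can be read as saying which records yield each patient's change. The arms would then be compared because the Objective and the randomisation say so. The choice of test may be in a statistical analysis plan that is not shown. Item 4 is weak evidence of intent, since a duration has no T1 and T2 and the groups are the only thing it could compare.

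Much of this stands. A reader might infer that the trial plans a before/after test in each arm and will judge the regimens by which one reaches significance. The Protocol says neither. The discordance figures in Step 1 are therefore the cost of a reading that the text allows, not of an analysis it prescribes. They also depend on d: near the peak they reach 50%, but at 0 and 1.0 SD they are about 10%, and at 1.2 SD about 2%.

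It would also be tempting to credit ANCOVA with its gain over T2 alone, which is 40% at r = 0.8 (0.449 against 0.748). Since the Protocol refers to T1 and T2, the fair comparator is the change score.

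The charitable reading does not, however, dispose of the unequal interval. If each patient's T1–T2 change on the item 10 records is the quantity compared between arms, Step 2 applies in full. The one escape is that pre-operative T1 means the initial film rather than the pre-elastics record. The Protocol does not say so, and item 10 points the other way.

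**Conclusion.** The point holds in a limited form. The wording for the primary cephalometric measures should be aligned with the between-arm Objective, and the baseline should be one that means the same thing in both arms. The documents do not support the claim that an invalid analysis has been specified.

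The false-signal risk of about 10–50% is conditional on separate within-arm tests, 15 per arm, two-sided 0.05, and an equal true change between 0 and 1.0 SD of change. The unequal interval follows from items 2, 5, 6 and 10 under Procedure, provided T1 is the pre-elastics record; its size is unknown. The precision gain from ANCOVA over a change score is modest: about 13% of the CI half-width at r = 0.5 and 5% at r = 0.8, both correlations being assumed. The better argument for the change is a comparable baseline, with precision second. This is a free improvement.

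**What to change.** Replace item 1 of Methods of assessment with wording such as: *For each cephalometric measure the two groups are compared on the T2 value, adjusted by ANCOVA for the value on the cephalogram taken before bonding, and the result is reported as a between-group difference with 95% CI. Within-group T1–T2 changes, including the change over the elastics phase, are descriptive only.* Define T1 at the same place, stating which film it is in each group.

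The same between-group wording can be used for casts, since study casts are among the initial records. For smile photographs, a pre-bonding baseline applies only if a standardised one exists: standardised smile photographs are listed only at item 10 under Procedure, while the initial records mention extra-oral and intra-oral photographs without that qualifier.

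The cost is a few lines of text. No extra patients, visits or cephalograms are needed, because the initial film is already taken for everyone. At most, the 15 initial films in group 2 must be traced for the same measures if that was not already intended.
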